¹⁵ Center for Universal Education at Brookings, June 2011, A Global Compact on Learning: Taking Action on Education in Developing Countries.

and competencies of young people (“education growth premium”) has resulted in sustained high rates of growth in developing countries. For young people, education enhances their ability to lead happier, healthier, and more productive lives.

A global review of research and programmes conducted by the Population Council (2009)¹⁶ on educating adolescent girls noted that “very few girl-friendly education programs have been evaluated.... Thus most approaches remain promising but unproven.” Hence there is a need for interventions that not only address service-related gaps and socio-economic barriers, but also that generate evidence to serve as a basis for advocacy with policy makers on scaling up strategies to increase participation of girls in secondary education.

The communities and schools in the intervention sites will be engaged in participatory explorations to better understand the service-related gaps and the socio-economic barriers that contribute to girls from marginalized communities dropping out of school. These stakeholders will also be involved in the designing the specific activities to address these gaps and barriers.

The intervention

The intervention will test innovations to address both service-related gaps and socio-economic barriers to girls’ completion of secondary school, and aims to reduce vulnerability to HIV and have long-term educational and livelihood benefits for adolescent girls.

The intervention is described in detail in Appendix 1. *Sabala Project Implementation Design*.

Usual care intervention: Girls in the control arm (73 high schools) will be provided with the standard level of care as currently provided by the government and other NGOs.

Enhanced intervention: In intervention communities, service-related gaps and socio-economic barriers to girl’s schooling will be addressed by:

1. Reducing the economic pressure that households face to withdraw girls’ from school by linking girls and their families to various government schemes and social entitlements;
2. Building appreciation and value of girls’ education within families and their local communities;
3. Enhancing family and community accountability for school attendance by working with the School Development and Management Committees (SDMCs);

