There will be 13 girls, on average, enumerated for each of two sequential cohorts in each intervention and control cluster. In effect, 26 girls will be enrolled in each cluster, 1 year apart, corresponding to a total sample of 1050 girls in the control arm and 1050 girls in the intervention arm. We assume that there is minimal loss to follow-up and that 28 girls are followed-up at the endline. With these data we will have 80% power to detect a ratio of around 33% for the transition from 7-8th standard and a 25% ratio for retention until 10th standard. We have included conservative estimates of the control outcome proportions, and reported calculations for a range of K from 0.1 to 0.25.

In order to measure the medium- and short-term outcome indicators for families, the families of the SC/ST adolescent girls recruited in both arms will be interviewed. To facilitate intervention at the family level, each SC/ST adolescent girl in both the arms will be profiled and the main decision maker will be identified. These decision makers will form the sampling frame to recruit the respondents at the family level.

The sample sizes for the girls are summarized in Table 3.

Table 3: Summary of sequential cohort study design

	May 2013	May 2014	February 2017	February 2018
Intervention site, cohort 1	525 girls completed 7 th standard and their families		Follow-up interviews	
Control site, cohort 1	525 girls completed of 7 th standard and their families		Follow-up interviews	
Intervention site, cohort 2		525 girls completed 7 th standard and their families		Follow-up interviews
Control site, cohort 2		525 girls completed 7 th standard and their families		Follow-up interviews

Allocation of clusters to intervention and control arms

68 villages were selected using systematic random sampling from the sample frame of 121.

[figure not shown]
Schools were allocated randomly to either receive the intervention immediately (experimental condition) or at a later date (waitlist control group). The villages were randomised into intervention and control arms so that 34 villages (62 high schools) in intervention and 34 villages (63 high schools) in control arms. This was done by initially selecting 34 villages randomly from the selected 68 villages using STATA 11. These selected 34 villages were allocated into intervention arm and the remaining 34 villages were allocated into control arm.

Accounting for potential contamination

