In the 4th year a total of 17 participants will be chosen from the list of policy makers identified at each level. The tool used for data collection will be a semi-structured interview guide. The leads and triggers will be developed around 1) knowledge on the goals, objectives, reach and strategies of the intervention; 2) the level of support in word and action from officials towards these intervention activities; 3) perceptions on applicability of intervention strategies for scale up; and 4) the description of any move by any government body to develop policies and guidelines based on this intervention model for scale.

Probe lists for all in-depth interviews are included in appendix 4

Intervention monitoring

A robust monitoring system will be used to monitor the activities at the school and community level as follows:

- (i) An individual tracking system which tracks individual girls will be developed to monitor inputs, outputs and certain outcome level indicators. The project will facilitate schools to track the girls from marginalized communities during the project period to monitor school achievement and ensure efficient identification of drop-outs, so that the issues related to drop outs can be effectively addressed.
- (ii) Within the communities, project activities such as linkages to the government schemes, school-to-community contact programs, support for tutorials/remedial classes etc. with adolescent girls and their families will be monitored.

[figure not shown]

Figure 1: Allocation of clusters. A total of 80 villages, each randomly allocated into intervention and control arm. Figure 1 illustrates the distribution of control and intervention clusters in the selected districts.

Time period

The total study period will be 4 years: 9 months of start-up activities and baseline assessments, 30 months of intervention, and another 9 months of final assessments and analyses.

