As this study will take place in government schools, in order to get the necessary permissions and directives for the schools in the study villages, KHPT has successfully advocated with the Department of Education at the State Level. The State Commissioner for the Department of Education has agreed to the intervention study and written to the education administrators at the district level in the two study districts, instructing them to support the study. They in turn will issue guidance and directives to all government schools in their districts to support the study, which includes directing that all teachers in the intervention schools attend training as part of the intervention. These government directives will help overcome the effects of any change in school administration during the course of the intervention. The co-operation of the school administration, staff and the SDMC is also being sought during the planning phase of the intervention..

For the case studies, at the end of the each session the interviewer will summarise the events lifeline with the help of the girl. In the next set of interviews the previous lifelines could be looked at the end of the session.

The study has excluded certain schools considering various technical and logistical aspects. The private and unaided schools were excluded from the study in order to ensure maximum reach to the intended communities, given the project resource constraints, and because they may not be amenable to external interventions. For the same reason urban and residential schools and schools with less than 10 SC/ST adolescent girls were also excluded. In order to ensure equity to all schools enrolled in the trial, we are applying for funding to enable the school based interventions be provided in these schools at the end of the intervention period.

As described above, the intervention is being carefully designed in order to ensure that it does not cause any unintended harm and that the changes in the community and the schools are sustained beyond the intervention period. The design has been finalized after many rounds of discussions with stakeholders at different levels. The design has attempted to take into consideration the existing structures, the regulatory environment and the cultural practices, and after ensuring buy-in of the major stakeholders, including the government.

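### Any roll-out to control schools is tied to the end of the intervention period rather than to completion of end line, so the plan allows controls to be exposed before they are measured

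*Protocol*

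**What the plan says.** - **Control condition.** Under The intervention: "Girls in the control arm (73 high schools) will be provided with the standard level of care as currently provided by the government". Services from NGOs count as well, and no end date is given for this.
- **Waitlist.** Under Allocation of clusters to intervention and control arms, schools receive the intervention immediately "or at a later date (waitlist control group"). The later date is not specified.
- **Trigger.** Ethical issues has the only text that gives a time. For the sake of equity among the schools that take part, it says that funding is being sought "to enable the school based interventions be provided in these schools at the end of the intervention period".
- **Phases.** Time period: "The total study period will be 4 years", made up of 9 months of start-up and baseline work, then "30 months of intervention, and another 9 months of final assessments and analyses". The same section gives the last 9 months to three months of end-line data collection and six months of analysis and reporting.
- **Dates.** Table 3 has baseline in May 2013 and May 2014, and follow-up interviews in February 2017 (cohort 1) and February 2018 (cohort 2).
- **A competing statement.** Sampling of the adolescent girls ends follow-up of every girl when year 4 begins.

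No section says that roll-out to control schools waits until end-line data collection is complete.

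**The concern.** A waitlist control is a valid comparator only while it is still waiting. Two of the four co-primary outcomes, marriage and first sexual intercourse, are read at end line and so keep accruing up to the interview. If control schools receive part of the programme before then, the difference between arms shrinks and the trial becomes more likely to miss a real effect.

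Elsewhere the protocol takes care on this point. It added 12 villages because 12 of those first allocated adjoined a village in the other arm, and it kept monitoring light in the control arm so as not to influence outcomes there. A roll-out trigger that can fall before measurement does not fit with that care.

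**Working it through.** **1. The plan's own total.** 9 + 30 + 9 = 48 months, which reproduces the stated 4 years. The intervention ends at month 9 + 30 = 39.

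**2. Order of events within Time period alone.** The intervention ends at month 39. If the three months of end line come first in the closing phase, they occupy months 40 to 42. The trigger therefore precedes end line, but by at most about three months.

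**3. Order of events against Table 3.** The start date is an assumption: May 2013 (cohort 1 baseline in Table 3) to July 2013 (first quarter of the activity chart).

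| Assumed start | Month 39 | Gap to February 2017 | Gap to February 2018 |
|---|---|---|---|
| May 2013 | August 2016 | 6 months | 18 months |
| July 2013 | October 2016 | 4 months | 16 months |

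Sensitivity of the gaps:
- If baseline collection adds three months to start-up, the cohort 2 gap is 13 to 15 months and the cohort 1 gap 1 to 3 months.
- If the intervention starts in August 2014 (February 2017 minus 30 months), the cohort 1 gap is zero and the cohort 2 gap 12 months.
- The cohort 2 gap reaches zero only with an intervention start in August 2015 (February 2018 minus 30 months).

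**4. Consistency of the calendar.** From May to July 2013, 48 months ends in May to July 2017, which is 7 to 9 months before the cohort 2 interviews in Table 3. The activity chart spans 20 quarters, or 60 months. The start of year 4 (month 36) is May to July 2016, three months before month 39; if follow-up ended there, controls would not be exposed.

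**5. Outcomes at risk.** On normal progression (assumption), cohort 2 enters 8th standard in 2014 and is in 10th standard in 2016-17. Entry into 8th is fixed for both cohorts before any roll-out. Marriage and first intercourse remain open in both cohorts until end line. Completion of 10th standard could be affected in cohort 2.

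**6. Check of the power formula.** The plan's cluster-count formula is
c = 1 + (1.96 + 0.84)² × [p0(1−p0)/m + p1(1−p1)/m + k²(p0² + p1²)] / (p0 − p1)².
For marriage with p0 = 0.30, p1 = 0.225, m = 28 and k = 0.20, the bracket is 0.00750 + 0.00623 + 0.00563 = 0.01935. Then c = 1 + 7.849 × 0.01935 / 0.005625 = 28.0, as the protocol tabulates.

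**7. Illustration of dilution.** Assumptions: marriage risk of 25% in unexposed controls, true risk ratio 0.75 (p1 = 0.1875), k = 0.20, 40 clusters per arm, 26 girls per cluster. Half the girls are in cohort 2 (525 of 1050 per arm), and only cohort 2 controls gain a fraction f of the effect.
- Control risk: pc = 0.25 − 0.5 × f × 0.0625.
- Power = Φ(|pc − p1| / √V − 1.96), where V is the bracket above, with pc in place of p0, divided by 39.

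| f | pc | Risk ratio | Observed reduction | Power |
|---|---|---|---|---|
| 0 | 0.2500 | 0.750 | 25% | 85% |
| 0.25 | 0.2422 | 0.774 | about 23% | 75% |
| 0.50 | 0.2344 | 0.800 | 20% | 63% |

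Across f = 0 to 0.50, power falls from 76.5% to 53.5% if control risk is 20%, and from 90.6% to 70.7% if it is 30%.

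**The case against.** A reader might infer that controls will be treated 16 to 18 months before they are measured. The documents do not support that, for these reasons:

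- **Roll-out is conditional.** The protocol says only that funding is being applied for.
- **Which schools are meant is not entirely clear.** The preceding sentences concern schools excluded from the trial. However, the sentence itself names schools enrolled in it, and intervention schools already have the programme, so with the waitlist text control schools are the natural reading.
- **The 16 to 18 months is derived.** It lays a 48-month schedule from an assumed start over a calendar running to 2018. Time period alone gives a gap of about three months at most, and ending follow-up at the start of year 4 gives none. The shading of the activity chart, which could date the intervention, is not legible in the text at hand.
- **Only school-based components are covered.** The intervention section lists two of these (teachers and tutoring) against five aimed at households, communities, girls and boys.
- **The girls would be leaving school.** On normal progression, cohort 1 would have left 10th standard before August to October 2016. Cohort 2 would have about 7 to 9 months left, taking May 2017 as the end of that school year. Girls already married or out of school cannot have those outcomes reversed.

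All of this limits the likely size, and makes half the effect look like a high assumption. It does not remove the point: the only stated trigger precedes end line under both Time period and Table 3, and nothing holds roll-out back until measurement is complete.

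**Conclusion.** The point holds as a defect in the stated trigger. The plan allows control girls to be exposed before marriage and first intercourse are measured in both cohorts, and possibly before completion of 10th standard in cohort 2. The direction of bias is toward no difference.

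The length of the window cannot be fixed from the document. It runs from none, if follow-up stops at the start of year 4, to 16 to 18 months for cohort 2 under Table 3 with a start in May to July 2013. The loss of power from about 85% to 75% or 63% is an illustration that rests on the assumed 25% to 50% gain in cohort 2 controls; the document gives no basis for choosing that fraction.

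A reader might also carry the dilution over to the detectable reduction of around 33% for transition from 7th to 8th standard. That would be wrong, because entry into 8th is settled before any roll-out could begin.

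The change should be made: the remedy is small and the bias could not be undone at analysis.

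**What to change.** 1. Reconcile the calendar across Sampling of the adolescent girls, Table 3, Time period with its activity chart, and Ethical issues. Give dates for the start and end of the intervention and for each cohort's end line.
2. In Ethical issues, and beside the waitlist statement under Allocation of clusters, state that any roll-out to control schools begins only after the last cohort 2 end-line interview is complete. Name control schools explicitly.

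This takes a sentence or two on roll-out plus the corrected dates. Sample size, outcomes and analysis do not change. The cost is a longer wait for control schools.

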SC/ST girls will be enumerated and included in the cohort. We will conduct a complete-capture enumeration of all SC/ST girls in all trial sites, therefore, all SC/ST girls will be approached for inclusion in the trial.

Families

All families of SC/ST girls will be included in the cohort.

Sample size

The sample size calculations are based on the four co-primary outcomes:

1. Percentage of those enumerated in 7th standard (the study cohorts) who ENTER into grade 8th
2. Percentage of those in the study cohorts who complete 10th standard
3. Proportion of girls in the study cohorts who are married at end line.
4. Proportion of girls in the study cohorts who experienced first sexual intercourse at end line

The sample size calculations are based on the parameters shown in the table below. The baseline numbers are found in the KSS Karnataka report for 2010-2011, a rural assessment by KHPT in 2013, the district level household surveys (DLHS) from 2007-2008, and the Integrated Biological and behavioral Assessment (IBBA) conducted by KHPT from 2006-2011. Broadly speaking, the expected effect sizes are guided by the aim of the intervention to bring the outcomes among SC/ST girls in-line with all girls. Therefore, we have used the prevalence of the outcomes in these surveys to estimate plausible effect sizes.

Parameter	Notes
Harmonic mean cluster size	This is based on an enumeration carried out in the 225 high schools located in 121 villages by KHPT. Approximately 15 SC/ST girls are available at each school
Refusal/loss to follow-up	Refusal and loss to follow-up are expected to be low, approximately 5-10% (14 girls per cluster is used in the calculation, multiplied by 2 to account for the two cohorts)
Between cluster variation (k)	The between cluster variation in the outcomes is not known. Therefore, we have reported sample sizes for a range of values.
Control arm proportions	

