We will consider two criteria, first is the criterion of the variance of the treatment effect and the second is a criterion of assessing change in treatment effect as defined as the difference between the crude and adjusted treatment effect. We plan to analyze both the variance of the estimated treatment effect and the extent to which the estimated treatment effect changes by adjusting for covariates (Raab and Butcher, 2001)²¹. The approach that will be used in this trial is to assess the extent to which the adjustment of covariates will affect the estimated treatment effect. If the allocation of treatments to units is imbalanced, it is likely to produce a substantial difference between the unadjusted and adjusted estimates of the treatment effect. Using the following general expressions, which Raab and Butcher (2001) developed, this will be overcome as follows.

The estimate of the treatment effect, without any adjustment for covariates, becomes a difference in weighted cluster means of the outcome as;

$$Y_{..2} - Y_{..1} = \frac{\sum_{j:t=2} w_j y_{.j}}{\sum_{j:t=2} w_j} - \frac{\sum_{j:t=1} w_j y_{.j}}{\sum_{j:t=1} w_j}$$

where the weights are $w_j = s^2 m_j / (s^2 + t^2 m_j)$ and s^2 and t^2 are the estimates of between- and within-cluster variances as noted respectively τ^2 and σ^2 , m_j be the number of members in the j th cluster, y_{ij} be the outcome of i th member of the j th cluster and t be the different trial arms (intervention or control) as denoted by 1 or 2.

The variance of the estimated treatment effect can be estimated by

$$s^2 [1/(\sum_{j:t=1} w_j) + 1/(\sum_{j:t=2} w_j)]$$

²¹ Gillian M. Raab, Izzy Butcher (2001), Balance in cluster randomized trials, *Statistics In Medicine*, Statist. Med. 2001; 20:351{365

The study will be estimating the change in treatment effect, when adjusted for the covariates using

$$\sum_{K=1,2,\dots,p} \beta_k (x_{k,2} - x_{k,1})$$

Where β_k is the estimate of regression coefficient for predicting y from the k^{th} covariate and $x_{k,t}$ is the weighted mean of the cluster means for treatment t for the k^{th} covariate, with weights w_j as defined above and p the number of covariates.

Analysis of primary outcomes

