At project completion, we will assess whether, at follow up, there are significant differences between the intervention and control girls in the key indicators of entering 8th standard, completing tenth standard, being married, having sexual debut and entering into sex work. In the course of the analysis we will present simple cluster summaries for the primary outcomes. We will perform statistical tests, using the t-statistic, to assess the significance of and differences observed between the arms.

The final analysis will assess whether the intervention and control schools, adolescent girls and their families significantly differ in terms of the intermediate and short-term outcomes. As recommended by Hayes and Moulton²², given the large number of clusters and because of reasons related to statistical efficiency, individual-level regression methods will be used to test for significant differences in outcomes between intervention and control arms. For each outcome of interest (e.g., the proportion of girls married at the end of the study period, the proportion of girls passing to 10th Standard, etc.), multivariable logistic regression models using generalized estimating equations (GEE)^{23,24} to address clustering at the school level will be estimated. Stata 11 will be used for all analyses. Similar methods will be used to compare short- and medium-term outcomes among SC/ST girls and their families between intervention and control arms.

Qualitative data analysis

The qualitative data will be transcribed and translated into English. Qualitative analysis packages (eg., NVivo9, ATLAS TI) will be used to identify key issues and themes emerging over time. These findings will be used along with the quantitative findings to understand the impact of the intervention.

Addressing confounding factors, selection bias, spill over effect and impact heterogeneity

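### The baseline-balance formulas label the between- and within-cluster variances the wrong way round; coded as labelled, they overstate the variance of the crude effect about 18-fold

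*Protocol*

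**What the plan says.** The subsection Assessing baseline balance (Protocol, Data entry and analysis) sets two criteria. The "first is the criterion of the variance of the treatment effect"; the second is the change between the crude and the covariate-adjusted effect.

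The crude effect is a difference of weighted cluster means, with weights w_j = s²m_j/(s² + t²m_j), where m_j is the number of girls in cluster j. The text then defines the two variances: s² and t² "are the estimates of between- and within-cluster variances as noted respectively" τ² and σ². Read in order, s² is the between-cluster variance τ² and t² the within-cluster variance σ².

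Next comes the sentence "The variance of the estimated treatment effect can be estimated by", followed by s²[1/Σw_j (arm 1) + 1/Σw_j (arm 2)]. The change-in-estimate criterion uses weighted covariate means "with weights w_j as defined above and p the number of covariates". No other part of the protocol restates or corrects the definitions.

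**The concern.** The formulas are inverse-variance formulas, so one of the two components has to be divided by the cluster size and the other not. It is the within-cluster component that averages out over the girls in a village. The labels give that role to the between-cluster component.

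An analyst who codes the definition as written would report a variance for the first criterion that is far too large, and would lose the weighting by village size in the crude effect and in the covariate means of the second criterion. That could mislead the judgement on whether adjustment changes the precision of the estimate, which is what the first criterion is for.

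**Working it through.** **Inputs (all Protocol)**
- Villages per arm: c = 40 (Summary of the sample size calculation results).
- Girls per village: m = 26 enrolled (same place); 28 in the sample size, where "14 girls per cluster is used in the calculation, multiplied by 2 to account for the two cohorts" (Sample size, parameter table).
- Central control proportion: p = 30% for retention (K and the number of clusters). The sample size tables span 9% to 40%.
- k: 0.10 to 0.25 (Summary of the sample size calculation results). The parameter table says that k is not known.
- Village-size distribution: not given. Sizes spread evenly over 20 to 40 girls are assumed below, for illustration only.

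**The plan's own figures.** The protocol gives no number for the balance variance. The inputs can be checked against its sample size tables. The Hayes–Bennett unpaired formula is

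c = 1 + (1.96 + 0.84)² × [p₀(1−p₀)/m + p₁(1−p₁)/m + k²(p₀² + p₁²)] / (p₀ − p₁)².

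With p₀ = 0.30, p₁ = 0.231 and m = 28 it gives 29.1, 33.3 and 38.6 for k = 0.15, 0.20 and 0.25, exactly as printed under Retention in school. So p, k and m are being used as the protocol uses them.

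**Which label fits the formula.** From the printed weights, s²/w_j = s²/m_j + t². For an inverse-variance weight this must equal the variance of a cluster mean, σ²/m_j + τ². Hence s² = σ² (within) and t² = τ² (between), the reverse of the text.

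**Size with equal clusters.** Take τ² = (kp)² and σ² = p(1−p) − τ².
- Intended: Var = 2(τ² + σ²/m)/c.
- As labelled: Var = 2(σ² + τ²/m)/c.

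For p = 0.30, k = 0.20, m = 26: τ² = 0.06² = 0.0036 and σ² = 0.21 − 0.0036 = 0.2064.
- Intended: 2(0.0036 + 0.2064/26)/40 = 0.000577, SE 0.024.
- As labelled: 2(0.2064 + 0.0036/26)/40 = 0.01033, SE 0.102.
- Ratio: 17.9 in variance, 4.2 in SE.

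**Sensitivity of the variance ratio**

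| p | k | m | ratio |
|---|---|---|---|
| 0.30 | 0.20 | 28 | 18.8 |
| 0.30 | 0.15 | 26 | 20.8 |
| 0.30 | 0.25 | 26 | 15.2 |
| 0.17 | 0.20 | 26 | 21.4 |
| 0.13 | 0.20 | 26 | 22.5 |
| 0.40 | 0.25 | 26 | 12.2 (smallest) |
| 0.09 | 0.10 | 28 | 27.2 (largest) |

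The last two rows are the extremes over p 9–40%, k 0.10–0.25 and m 26–28. Taking σ² = p(1−p) without subtracting τ² moves the lower end to 12.5 and leaves the upper end at 27.2.

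**Weights with unequal clusters** (assumed 20 to 40 girls, p = 0.30, k = 0.20)
- Intended weights: 14.83 for 20 girls, 23.56 for 40 girls, ratio 1.59.
- As labelled: 0.017427 and 0.017434, ratio 1.0004.
- True variance of the crude effect: 0.000529 with the intended weights, 0.000538 with the as-labelled weights, a loss of 1.8%.
- Variance that would be reported as labelled: 0.01033, about 19 times the true 0.000538.

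**The case against.** The strongest reply is that the sentence is clumsy rather than wrong. The word respectively stands next to the Greek letters and could tie only between to τ² and within to σ², which is the usual notation. The Latin letters would then be the estimates of their Greek counterparts, s for σ and t for τ, and everything would fit. That is very likely what was meant. It is not what the sentence says: the three pairs (s² and t², between and within, τ² and σ²) appear in parallel order, and words and symbols agree with each other in contradicting the algebra.

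Second, the inflation is hypothetical. It appears only if the labels are coded literally, and an SE near 0.10 with 40 villages per arm should strike an experienced analyst as implausible. This stands, and the 18-fold figure has to be read as conditional.

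Third, the section singles out the change in the estimate as the approach to be used, and that criterion uses only the weights, where the real loss is small. This also stands in part, but the same section says that both the variance and the change will be analysed, so the variance criterion remains in the plan.

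Fourth, no threshold is attached to the variance, and no trial conclusion depends on it. Under Analysis of primary outcomes the protocol says "We will perform statistical tests, using the t-statistic, to assess the significance of and differences observed between the arms", on simple cluster summaries, with GEE logistic models alongside. Neither uses these formulas, nor does the sample size. This is correct and sets the limit of the point.

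**Conclusion.** The definition is wrong as written: s² must be the within-cluster and t² the between-cluster variance. This follows from the protocol's own formulas and needs no outside source.

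The consequence depends on literal coding. In that case the variance of the crude effect is overstated by a factor that is about 18 at central inputs and lies between 12.2 and 27.2 over the protocol's ranges of p, k and m. The direction is the same throughout. The crude point estimate stays valid, as a nearly unweighted difference of village means, and the true loss of precision is about 1.8% under the assumed village sizes. The harm is therefore limited to the baseline-balance assessment. The point should be corrected, but it does not threaten the primary analysis.

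**What to change.** Reword the definition so that s² and t² are the estimates of the within- and between-cluster variances, σ² and τ² respectively. Leave the weight and variance formulas as printed. Then check that the code for the weights, the variance of the crude effect and the weighted covariate means follows the corrected definition. The cost is one line of wording and a short code check; nothing in the design, the data collection or the primary analysis changes.
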